5 MODIFICATIONS

5.1 Modifications to the Approved Clinical Study Protocol

There are no modifications from the clinical study protocol (Version 8, dated June, 24 2022) that impact statistical analysis.

5.2 Modifications to the Approved Statistical Analysis Plan

This is the first version of the SAP for the analysis.

6 STATISTICAL ANALYSIS

6.1 General Considerations

6.1.1 General Analysis Conventions

Categorical variables will be presented as counts and percentages of non-missing values. Continuous variables will be presented as means, standard deviations, medians, as well as minimums and maximums, and the number of non-missing values. Missing data will be handled as outlined in section 6.8. Unscheduled assessments will not be included in analyses, but may be included in listings. Appropriate rounding will be performed for the summary statistics. The number of significant digits for the mean and standard deviation will be one and two more than the number for the reported values, respectively. Minimum and maximum values will be presented with the same precision as the original data. Percentages will be presented with one decimal. All statistical tests will be two sided unless stated otherwise. Histograms will be used to assess the normality of the data. Unless otherwise specified below, baseline values will be the last collected value prior to device use.

Statistical tests used will be two-sided, with $\alpha=0.05$ as the level of significance. An absolute magnitude of the correlation coefficient that is 0.1-0.29 indicating weak correlation, 0.3-0.49 as moderate correlation and 0.5-1.0 as strong correlation.

6.1.2 Documentation conventions

The analyses described in this SAP as well as production of tables and listings will be performed using Version 9.4 (or newer) of SAS on Linux operating system. Additional statistical software may be used as needed.

6.1.3 Verification of results

All tables, listings, and graphs will be verified and reviewed before considered final. The verification process will ensure that the numbers are produced by a statistically valid method and that the execution of the computations is correct. Suitably qualified personnel will perform the verification procedures.

6.2 Background Characteristics

6.2.1 Subject Disposition

The number of subjects in the study population the number of subjects who completed and prematurely discontinued the study will be presented. Reasons for premature discontinuation or withdrawal from the study will be summarized in a listing.

6.2.2 Demographics and Medical History

Baseline demographic and medical history data will be summarized by treatment group with descriptive statistics [non-missing values (n), mean, standard deviation (SD), standard error of mean (SEM), median value, maximum value, and minimum value] for quantitative parameters and with counts and percentages

(or proportions) for categorical parameters using both the ITT and AT populations including appropriate p values to test the effectiveness of randomization. A listing will also be provided.

6.3 Primary Endpoint Analyses

P1: Compare the trajectory of the median Abbott ICD and CRT-D device measured daily PA obtained over the 1 month before randomization (baseline) and week 4, week 8, and week 12 after randomization among patients randomized to remote CR versus usual management.

Analysis strategy for P1: The outcome variable for this objective is the median Abbott ICD and CRT-D device measured daily PA obtained over the 1 month before randomization (baseline) and week 4, week 8, and week 12 after randomization. This endpoint represents a summary measure. The hypothesis test will evaluate whether the trajectory of the mean Abbott ICD and CRT-D device measured in the remote CR treatment group is different from the trajectory in the usual management group. The test will be a multilevel modeling (aka mixed models) on trajectories of the outcomes over the study period. In the multilevel model, time (week of study), treatment group, and the interaction between treatment group and time will be handled as fixed effects. Time will be modeled as a continuous variable. The model will include random effects for subject-specific intercepts and slopes, with unstructured covariance for random intercepts and slopes.

Reporting for P1: Descriptive summaries of the median physical activity at baseline and 4 weeks, 8 weeks, and 12 weeks after randomization will be presented by treatment group. The estimated difference in slopes of trajectories from the CR and usual care treatment groups will be presented, along with the p-value for comparing the trajectories over the study period. If differences are noted with regard to baseline covariates adjusted analyses will be performed for the primary endpoint.

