4.2 Sample Size and Power

Sample size was determined based on the following power calculations:

For aim 1, a sample size of 28 subjects with 1:1 randomization each measured at 4 time points provides 81.1% power to detect a 15 minute per day difference in PA between groups at week 12 with a standard deviation of 19 minutes per day within each group and a within subject correlation of 0.7. A test based on a mixed-model analysis is anticipated at a significance level of 0.05.

For aim 2, a sample size of 50 subjects with 1:1 randomization provides 80.2% power to detect an 8% difference in KCCQ score between groups with a standard deviation of 10 in KCCQ score within each group and an alpha of 0.05.

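### The primary PA model leaves the arms free to differ at the pre-randomisation baseline: the slope test is valid, but a common-baseline model is usually more precise at no cost

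*SAP*

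**What the plan says.** The P1 outcome in SAP 6.3 is median PA, "measured daily PA obtained over the 1 month before randomization (baseline) and week 4, week 8, and week 12 after randomization", so the pre-randomisation value is a response and not a covariate. On the fixed effects the SAP says: "time (week of study), treatment group, and the interaction between treatment group and time will be handled as fixed effects". It adds "Time will be modeled as a continuous variable" and "The model will include random effects for subject-specific intercepts and slopes, with unstructured covariance for random intercepts and slopes". The reported comparison is the interaction: "The estimated difference in slopes of trajectories from the CR and usual care treatment groups will be presented". SAP 6.3 gives no numeric code for the baseline month.

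For aim 1, SAP 4.2 plans for "a sample size of 28 subjects with 1:1 randomization each measured at 4 time points". It states that this design "provides 81.1% power to detect a 15 minute per day difference in PA between groups at week 12", assuming a "standard deviation of 19 minutes per day within each group and a within subject correlation of 0.7".

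Two other provisions touch on baseline. SAP 6.7 (and Protocol 11.12) adds the baseline mean as a covariate in a sensitivity analysis, for which SAP section 7 lists no table. SAP 6.3 also allows adjusted analyses if differences in baseline covariates are noted. Neither sets the arms equal at baseline. Protocol 11.8.1 describes a mixed model for the trajectories but lists no fixed effects.

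**The concern.** If baseline is coded as time 0, the treatment-group coefficient is the arm difference before anyone was treated. Allocation is randomised 1:1, so the expected value of that difference is zero, yet the model spends a parameter on estimating it. Under the planning covariance, a patient's fitted starting level and fitted slope are negatively correlated, because noise that lifts the baseline value flattens the fitted slope. An arm that starts high by chance therefore tends to show a smaller slope. Fixing one baseline mean for both arms uses that correlation to sharpen the slope contrast and to correct for the chance imbalance.

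At stake is the precision of the primary estimate in a very small trial. Protocol 9.1 says the results will be used to design a pivotal trial.

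**Working it through.** **Inputs (SAP 4.2, 6.1.1, 6.3).** 14 per arm; times 0, 4, 8 and 12 weeks; SD 19, so total variance 361; correlation 0.7; 15 min/day at week 12; two-sided alpha 0.05. Assumed: baseline at time 0, equal variance at all four times, complete data and, to begin with, no random-slope variance.

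**Variance components.** Between patients: 361 × 0.7 = 252.7. Residual: 361 × 0.3 = 108.3. The mean time is 6 weeks and Sxx = 36 + 4 + 4 + 36 = 80.

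**Least-squares fit for one patient.**
- var(slope) = 108.3/80 = 1.354
- var(intercept) = 252.7 + 108.3 × (1/4 + 36/80) = 328.5
- C = cov(intercept, slope) = -108.3 × 6/80 = -8.12

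**The plan's own figure.** With a free baseline difference, var(slope difference) = (2/14) × 1.354 = 0.1934. The 12-week SE is 12 × √0.1934 = 5.28. Power = Φ(15/5.28 - 1.96) = 81.1%, which is the SAP's figure. The sample size was therefore computed for exactly this free-intercept slope test.

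**Common baseline.** The variance per patient becomes 1.354 - 8.12²/328.5 = 1.153, a ratio of 0.852 (a cut of 14.8%). SE = 12 × √((2/14) × 1.153) = 4.87. Power = Φ(15/4.87 - 1.96) = 86.9%. With a t test, power goes from 78.1% to 84.2%.

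**Shift given imbalance.** For an observed baseline difference d, the expected move in the 12-week contrast under the planned model is 12 × C/361 × d = -0.27d. One SE of baseline difference is 19 × √(2/14) = 7.18 min/day, which moves the contrast by 1.9 min/day, or 13% of the 15-minute target. Under the common-baseline model the move is zero if the fitted covariance is right.

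**Other sample sizes in the documents.**

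| N | SE, planned | SE, common baseline | Power, planned | Power, common baseline |
|---|---|---|---|---|
| 13 (SAP 4.1; 7/6 split assumed) | 7.77 | 7.17 | 48.8% | 55.3% |
| 28 (SAP 4.2) | 5.28 | 4.87 | 81.1% | 86.9% |
| 50 (protocol synopsis) | 3.95 | 3.64 | 96.7% | 98.4% |

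At N = 13 a t test on 11 df gives 42.2% and 48.0%. One SE of baseline imbalance is then 10.57 min/day, and the shift is 2.9 min/day (19% of target).

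**Sensitivity to the covariance (assumed values).** With random slopes of SD s (min/day per week) and intercept-slope correlation r, var(slope) = 1.354 + s² and C = r × 15.9 × s - 8.12. The variance cut is C²/(328.5 × var(slope)), and the shift per minute is 12C/361.

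| s | r | Variance cut | Shift per 1 min/day |
|---|---|---|---|
| 0.5 | -0.3 | 21% | -0.35 |
| 0.5 | 0 | 12.5% | -0.27 |
| 1.0 | -0.3 | 21% | -0.43 |
| 1.0 | 0 | 8.5% | -0.27 |
| 1.0 | +0.3 | 1.5% | -0.11 |
| 1.0 | +0.5 | about 0% | about 0 |

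If the month-long baseline has half or a quarter of the weekly residual variance, and both estimators keep their equal-variance weights, the cut is 7.3% or 1.6% and the planned model's shift is -0.16 or -0.09 per minute. If only the correlation changes, with no random slopes, the variance ratio is 0.735 at 0.5 and 0.953 at 0.9.

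**Does SAP 6.7 cover it?** In four simulated complete data sets (random-intercept fit), adding baseline as a covariate while keeping it as an outcome left the slope estimate and its SE unchanged to three decimals. A covariate that is constant over time acts on a patient's level and not on the slope contrast.

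**The case against.** The strongest reply is that this is a standard, valid model and the concern is about efficiency. That stands. The stated power also belongs to this very test, so plan and sample size agree, and the study calls itself hypothesis generating.

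A reader might infer that the planned test is biased, that it inflates type I error, or that it throws the baseline data away. The documents support none of these. Over randomisations the slope difference is unbiased. Baseline stays in the model, and at correlation 0.7 about 73% of any imbalance cancels. Only the known equality of the arms goes unused.

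The size of the gain is also open to challenge. SAP 6.3 specifies an unstructured intercept-slope covariance, and a positive correlation can remove the gain. With s = 1.5 and r = +0.5 the shift even changes sign, to +0.13. The SAP's baseline is a one-month summary, while Protocol 11.5 takes the later points from single weeks, so baseline may well be less noisy. (Protocol 11.8.1 says one week.) In that case the common-baseline model is free of carry-over only if its fitted covariance reflects the difference. With half the residual variance at baseline and equal-variance weights, its own shift would be 12 × (-0.0132 + 0.0247 × 0.947) = +0.12 per minute. Here 0.0247 is 8.12/328.5, and -0.0132 and 0.947 are the expected slope and intercept differences per minute of imbalance. This is a reason to keep both models in view.

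Finally, dropping the group term means equal baselines only if baseline is time 0. If the baseline month were coded at its midpoint, about week -2, the same edit would impose equality after the baseline period. The fix therefore has to state the coding.

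**Conclusion.** The point holds as a worthwhile, inexpensive improvement and not as an error in the test. With the SAP's own inputs, the common-baseline model cuts the variance of the slope difference by about 15% and adds about 6 points of power at N = 28. It also removes an expected shift of 0.27 min/day per 1 min/day of chance imbalance. These figures rest on equal variances, complete data, no random-slope variance and baseline at time 0. With random slopes correlated with intercepts, or a quieter baseline, the cut lies between about 0% and 21% and the shift can be near zero.

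A reader might also hope that the change makes up for a small sample. It does not: at 13 patients power stays near 55% at best under these inputs.

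The point concerns the slope test in SAP 6.3. Protocol 11.3 words study success as a change in mean from baseline to week 12, and that difference in wording is a separate matter.

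**What to change.** In SAP 6.3:
- Code baseline as time 0.
- Remove the treatment-group main effect so that both arms share one baseline mean.
- Keep time, the treatment-by-time interaction, and the random intercepts and slopes.
- Take the primary slope difference and its p-value from this model.
- Keep the unconstrained model as a sensitivity analysis.

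Protocol 11.8.1 has no list of fixed effects from which to remove a term, so add a sentence there that states the common-baseline model.

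The cost is a sentence or two in each document. No new data or patients are needed, and randomisation justifies the constraint.

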### 3 STUDY OBJECTIVES

### 3.1 PRIMARY OBJECTIVE

The primary objective is to test the efficacy of a weekly patient tailored remotely administered exercise prescription to increase the CIED measured weekly physical activity level in patients with HF and previously implanted cardioverter-defibrillator (ICD) or cardiac resynchronization therapy defibrillator (CRT-D) CIEDs manufactured by Abbott medical.

The PA data will be gathered by the CIED and provided to the study database in a structured format by Abbott Medical. The primary endpoint data will be recorded daily for the entire enrollment period of 16 weeks. Weekly averages will be calculated and compared across groups. Clinical and demographic information gathered at baseline will be used to ensure randomization was effective at balancing patient comorbidities. Adjusted analyses will be used to adjust for residual differences.

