### 3.2 SECONDARY OBJECTIVES

- Baseline and follow up KCCQ quality of life survey scores will be compared between treatment groups.
- To assess safety of the intervention, we will report AEs between treatment groups.

No adjusted analyses will be performed for comparisons of secondary outcomes.

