### 8.2 PARTICIPANT MEDICAL HISTORY

Targeted Medical History will be collected at baseline.

The following elements of past medical history will be collected to describe the patients and ensure randomization was effective at balancing covariates of interest:

- Etiology of HF (ischemic versus non-ischemic)
- LVEF
- Baseline NYHA Class
- Previous Revascularization
- History of MI
- Moderate or Severe Valvular Disease (Aortic or Mitral)
- Baseline Medications (ACE Inhibitor, Beta blocker, ARNI, digoxin, loop diuretic, statins)
- Diabetes
- Hypertension
- BMI
- A fib or A flutter
- PHQ-9 Depression Screen
- Baseline Systolic and Diastolic BP (measured by cuff at home)
- Device type (ICD versus CRT-D)
- Baseline daily PA duration (minutes)
- Baseline day and night heart rate

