## 11.2 BASELINE DESCRIPTIVE STATISTICAL ANALYSIS

For the baseline descriptive summaries, continuous variables will be summarized using number of observations (n), mean, standard deviation (SD), median, 25th and 75th percentiles, minimum, and maximum.

All categorical variables will be summarized using frequency counts and percentages. The calculation of percentages will be based on the number of patients with non-missing measurements for that time point in the corresponding category. P values for Wilcoxon rank sum test or Pearson chi-square test or Fisher's exact test will also be reported.

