6.4 Secondary Endpoint Analysis

S1: Compare the change in mean HF symptom severity scores at baseline and 12 week as measured by Kansas City Cardiomyopathy Questionnaire (KCCQ) among patients randomized to remote CR versus usual management.

Analysis Strategy for S1: The outcome variable for this objective is the mean change in HF symptom severity scores from 1 week before randomization (baseline) to 12 weeks, calculated as the HF symptom severity scores in week 12 minus the mean of baseline period. The hypothesis test will evaluate whether the mean change in the remote CR treatment group is different from the mean change in the usual management group. The test will be a two-sample t-test allowing for unequal variances.

Reporting for S1: Descriptive summaries of the mean physical activity at baseline and 12 weeks, as well as the 12-week change mean will be presented by treatment group. The summary statistics of the score at baseline, at 12-weeks and change from baseline will be reported for each treatment group. The mean difference (95% CI) between the CR and usual care treatment groups for change from baseline will be presented, along with the t-test p-value. If differences are noted with regard to baseline covariates adjusted analyses will be performed for the Secondary endpoint.

S2: (Safety) Report Adverse Events of heart failure hospitalization, fracture, myocardial infarction, serious adverse arrhythmia, and ICD therapy among randomized patients .

Reporting for S2: A listing of Adverse Events will be produced for the study population.

S3: Investigate the correlation between change in daily PA as measured by the Abbott ICD or CRT-D device between baseline and week 12 after randomization and change in HF symptoms severity scores as measured by KCCQ during same time period.

Analysis Strategy for S3: The variables used for this objective are the change in median PA from baseline to week 12, and the change in HF symptom severity score from baseline to week 12. The hypothesis test will evaluate whether there is a correlation between these two variables, pooling subjects across treatment groups..

Reporting for S3: We will be reporting the strength of the correlation and related p value and 95% CI.

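### An adjusted primary analysis is run only if baseline imbalance appears, with no covariates or model form named, and the documents conflict on adjusting secondary endpoints

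*SAP*

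**What the plan says.** **Primary endpoint.** SAP 6.3 sets out the P1 model: fixed effects for time (continuous), group and group-by-time, with random intercepts and slopes and no covariates. Under the reporting paragraph it adds: "If differences are noted with regard to baseline covariates adjusted analyses will be performed for the primary endpoint". Protocol 11.8.1 carries the same sentence. Protocol 3.1 gives the purpose: "Adjusted analyses will be used to adjust for residual differences". SAP 6.7 separately plans a P1 sensitivity model with baseline PA as a covariate, which does not depend on any imbalance.

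**Baseline testing.** SAP 6.2.2 calls for "appropriate p values to test the effectiveness of randomization", in both the ITT and as-treated populations. Protocol 11.2 says: "P values for Wilcoxon rank sum test or Pearson chi-square test or Fisher's exact test will also be reported". Protocol 8.2 lists 16 baseline items, "collected to describe the patients and ensure randomization was effective at balancing covariates of interest", and Protocol 4.4 adds demographics and further history.

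**Secondary endpoints.** Protocol 3.2 states: "No adjusted analyses will be performed for comparisons of secondary outcomes". SAP 6.4 states, for S1: "If differences are noted with regard to baseline covariates adjusted analyses will be performed for the Secondary endpoint". Protocol 11.8.2 agrees with SAP 6.4 and so disagrees with Protocol 3.2. SAP 5.1 declares no protocol modification that affects the analysis.

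**Success.** Protocol 11.3 ties success to a significant P1 difference in the ITT population and does not say whether the result is adjusted or unadjusted. Sex and aetiology stratify the randomisation (SAP 4.3) but enter no planned model.

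**The concern.** After sound randomisation, a baseline difference between arms is chance. Its p-value does not show whether the variable predicts physical activity or KCCQ score. A rule that adjusts only for variables that happen to differ therefore selects on the wrong property, and may leave out a strong predictor that is balanced. The two factors that design would put first, sex and aetiology, are in no model.

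The rule also leaves the adjusted model to be built once the baseline table by arm is in hand, in an unblinded trial. It gives no threshold, no covariate list, no statement on time interactions and no order of precedence. The result could be a second P1 estimate whose form nobody can check against the plan. Protocol 9.1 says the results will be used to design a pivotal trial, so the status of each estimate should be clear.

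On the secondary endpoints an analyst cannot comply with Protocol 3.2 and SAP 6.4 together once a difference has been noted.

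**Working it through.** **1. What the sample size was built on.** Inputs from SAP 4.2: 28 patients (14 per arm), four time points, 15 min/day at week 12, SD 19, within-subject correlation 0.7, alpha 0.05. Assume equally spaced times coded 0 to 3 (sum of squares about their mean = 5) and equal correlation between all times.

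- SD of a patient's slope = 19 × √((1 − 0.7)/5) = 4.654 per interval.
- Slope difference = 15/3 = 5.
- Standard error = 4.654 × √(2/14) = 1.759, and 5/1.759 = 2.842.
- Power = Φ(2.842 − 1.96) = Φ(0.882) = 81.1%.

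This reproduces the stated 81.1% (78.1% with the t distribution). The figure matches a slope contrast with no covariates.

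**2. What a covariate main effect does to P1.** With complete data all patients share the same four times, so each contributes one intercept and one slope. A baseline covariate entered as a main effect shifts intercepts only. The slope part of the model still contains group alone, so the group-by-time estimate remains the difference in mean patient slopes.

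The SAP model was fitted to six simulated complete datasets (N = 14, 28 and 50). Adding an imbalanced covariate as a main effect left the slope difference identical to four decimals in all six; at N = 28 it was 5.3751 with p = 0.004 both ways. A separate refit found only trivial movement in the p-value. Adding covariate-by-time did move the result: in one N = 50 dataset the slope difference went from 4.84 (p = 0.004) to 1.89 (p = 0.29).

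Missing weeks break the exact identity. In a small simulation (N = 13, 50 runs per setting, assumed 10-20% missing weeks and assumed variances), the main effect moved the slope p-value by 0.02 to 0.06 on average.

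**3. How often the trigger would fire by chance.** Assume that a difference means p<0.05 and that tests are independent. The documents state neither. The chance of at least one is 1 − 0.95^k. The count of 23 takes Protocol 8.2 with its six medications, two blood pressures and two heart rates listed separately (16 + 5 + 1 + 1). About 32 adds the items from Protocol 4.4.

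| Variables tested (k) | Chance of at least one |
|---|---|
| 16 | 56.0% |
| 23 | 69.3% |
| about 32 | 80.6% |

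Leaving out the stratified factors gives 53.7%, 67.6% and 78.5%.

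**4. What that does to type I error.** Simulation under no treatment effect: 10,000 runs per setting, N = 13, 28 and 50, 16 or 21 independent normal covariates, one summary outcome, adjusting for every covariate with p<0.05.

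| Rule for declaring success | Type I error |
|---|---|
| Unadjusted test only | 4.5-5.5% |
| Adjusted result replaces unadjusted when triggered | 3.8-5.2% |
| Either result may count | 5.8-7.7%, largest at N = 13 |

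**5. Secondary endpoints side by side.**

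| Place | Adjustment of secondary endpoints |
|---|---|
| Protocol 3.2 | None |
| Protocol 11.8.2 | If baseline differences are seen |
| SAP 6.4 (S1) | If baseline differences are seen |

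The conflict lies within the protocol as well as between the two documents.

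**The case against.** The strongest reply is that the primary test is not open. SAP 6.3 specifies the unadjusted model in full, the adjusted analysis appears only under reporting, and SAP 6.7 refers to a main analysis and main results. A reader might infer that the primary model is chosen after looking at unblinded data. The documents do not support that: only the supplementary model is data-driven, and its trigger is baseline imbalance, not outcome. This part of the reply stands.

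A reader might also take 56-69% as a false-positive rate. It is only the chance that the trigger fires, under an assumed threshold that neither SAP 6.3 nor Protocol 11.8.1 states. Neither section links the trigger to the baseline p-values. Independence is doubtful too: the Protocol 8.2 list includes ischaemic aetiology with prior MI and revascularisation, and systolic with diastolic pressure. Nor are the figures a ceiling, since Protocol 4.4 adds more variables. This stands as well.

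It is also fair that a main-effect adjustment is not strictly inert when weeks are missing, that a baseline-PA model is already planned whatever the baseline table shows, and that both documents call the study hypothesis generating (Protocol 11.8.3, SAP 6.5).

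Three things survive. The covariates and form of the adjusted analysis are unspecified and selected by imbalance. Protocol 11.3 does not say that the unadjusted result decides. The secondary-endpoint passages contradict each other.

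**Conclusion.** The point holds as a defect of specification with modest consequences. The contradiction on secondary endpoints is certain and needs no assumption. For P1, the triggered analysis adds little as a main effect. It can change the answer only through time interactions that the plan does not mention.

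A reader might infer that the plan as written runs at 6-8% type I error. It does not say that either result may count. If the unadjusted test alone decides, there is no inflation, and replacing it by the adjusted result gave none of note either. The exposure comes from the silence of Protocol 11.3.

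The error rates rest on independent normal covariates, a p<0.05 trigger and a single summary outcome in place of the full multilevel model. The invariance of the slope estimate rests on complete data. The wording is worth correcting before analysis, but the flaw does not undermine the prespecified main test.

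**What to change.** 1. Delete the imbalance trigger in SAP 6.3 and 6.4 and in Protocol 11.8.1 and 11.8.2. Bring Protocol 3.1 (adjusting for residual differences) and Protocol 3.2 into line. Drop the between-arm baseline p-values in SAP 6.2.2 and Protocol 11.2, keeping the descriptive summaries.
2. State in Protocol 11.3 and SAP 6.3 that the unadjusted ITT slope test decides P1 success. Name the supportive models in advance and run them whatever the baseline table shows: the already planned baseline-PA model and, only if the final sample size allows, one with sex, aetiology and their time interactions.
3. Analyse S1 by ANCOVA with the baseline KCCQ score as covariate, in place of the t-test on change in SAP 6.4. The score is already collected.
4. Label any other adjustment, including one for an unexpected imbalance, as post hoc.

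**Cost.** Wording in the SAP and a protocol amendment; no new data or procedures. The S1 covariate uses one degree of freedom. Sex, aetiology and their time interactions add four fixed effects to the four in the P1 model (intercept, time, group, group-by-time). That matters if N is the 13 in SAP 4.1: two binary factors make four strata, or 13/4 = 3.25 patients per stratum across both arms. This is why that model is conditional on sample size.
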